Exclusion Criteria	
 1. Pregnant or breastfeeding. 2. Subjects with thoracic implantable devices, including pacemakers or other electronic implants. 3. Chronic, continuous ventilator support, which uses bi-level positive airway pressure (PAP) to improve lung function for severe conditions. (However, intermittent PAP, for non-pulmonary conditions, such as sleep apnea, is permitted). 4. Prior pneumonectomy. 5. Severe bronchiectasis (with FEV1 <30%) or disease deemed to be too severe in the opinion of the investigator. 6. Clinical or imaging findings consistent with an active pulmonary infection. 7. Platelet count \leq 50,000/mm³. 8. Subjects with uncorrectable coagulopathy at time of screening. 9. Subjects medically unable to stop anti-platelet agents (e.g., aspirin, clopidogrel, prasugrel, ticagrelor) at least 5 days prior to the procedure through 48-72 hours after the procedure. 10. Subjects medically unable to stop warfarin at least 3-5 days prior to the ablation procedure, or until INR \leq 1.5, through 48-72 hours after the procedure. On the day of the procedure, subjects with an INR $>$ 1.5 cannot have the procedure completed that day but may be rescheduled or postponed. 11. Subjects medically unable to stop anticoagulants (e.g., rivaroxaban, apixaban, dabigatran, edoxaban) at least 3 days prior to the ablation procedure through 48-72 hours after the procedure. 12. Subjects who require heparin or low molecular weight heparin bridging. 13. Expected survival less than 6 months, in the opinion of the investigator and/or treating oncologist. 14. Subjects with known or suspected brain metastases. 15. Subject has had any radiation (i.e., SBRT or EBRT) to the intended ablation zone. 16. Endobronchial tumors proximal to and including the segmental airways. 17. Tumors where the anticipated zone of ablation would encompass significant (in the opinion of the treating physician) emphysematous or bullous disease. 18. Subject who underwent lung ablation, surgical resection therapy, radiotherapy, or any other treating procedure within 30 days prior to the planned study ablation procedure or those who plan to receive a lung ablation, surgical resection, or

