	
radiation therapy on the ablated lung side before completing the primary endpoint assessment (30 days post-ablation).
 
19. Subject who received systemic therapy (e.g., chemotherapy, targeted drug therapy, or immunotherapy) within 14 days prior to the planned study ablation procedure or those who plan to receive systemic therapy before completing the primary endpoint assessment (30 days post-ablation).
 
20. Uncontrolled hypertension pre-procedure (Visit 2). Defined as systolic blood pressure \geq 160mmHg and/or diastolic blood pressure \geq 100mmHg despite pharmacotherapy.
 
21. Subjects who have participated in an investigational drug or device research study within 30 days of enrollment that would interfere with the primary endpoint of this study.
 
22. Physical or psychological condition that would impair study participation.
 
23. Severe neuromuscular disease.
 
24. Subjects judged unsuitable for study participation by the Investigator for any other reason.
 
Intra-operative exclusion criteria that lead to stopping a procedure:
 
25. Inability to tolerate anesthesia.
 
26. Time of navigation to initiation of ablation longer than 60 minutes, per target tumor.
 
27. Bleeding estimated to exceed 50cc (visualization via the drainage system) or a Nashville grade 2 or higher intervention is required (see Appendix 2).
 
28. If the CBCT imaging after a bleeding episode obscures the radiographic visibility of the tumor such that the ablation probe/tumor relationship is not discernable, the procedure should be terminated.
 
29. Any presenting condition discovered intra-procedurally that in the opinion of the Investigator would make participating in this study not in the subject's best interest.

DSMB (Data Safety Monitoring Board)	
An independent Data Safety Monitoring Board (DSMB) will be commissioned to periodically review safety events from the study to ensure safety trends are consistent with the current safety profiles of the devices.
 
Specifically, a report of death or severe hemorrhage requiring intervention beyond local therapy (i.e., Nashville \geq grade 2 or CTCAE \geq grade 2) within 30 days of an ablation procedure will temporarily stop enrollment and require review by the DSMB.

Statistical Analyses	
The number and percentage of tumors achieving Technique Efficacy will be summarized and a confidence interval will be estimated.

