19. Subject who received systemic therapy (e.g., chemotherapy, targeted drug therapy, or immunotherapy) within 14 days prior to the planned study ablation procedure or those who plan to receive systemic therapy before completing the primary endpoint assessment (30 days post-ablation).
20. Uncontrolled hypertension pre-procedure (Visit 2). Defined as systolic blood pressure $\geq 160\text{mmHg}$ and/or diastolic blood pressure $\geq 100\text{mmHg}$ despite pharmacotherapy.
21. Subjects who have participated in an investigational drug or device research study within 30 days of enrollment that would interfere with the primary endpoint of this study.
22. Physical or psychological condition that would impair study participation.
23. Severe neuromuscular disease.
24. Subjects judged unsuitable for study participation by the Investigator for any other reason.

Intra-operative exclusion criteria that lead to stopping a procedure:

25. Inability to tolerate anesthesia.
26. Time of navigation to initiation of ablation longer than 60 minutes, per target tumor.
27. Bleeding estimated to exceed 50cc (visualization via the drainage system) or a Nashville grade 2 or higher intervention is required (see Appendix 2).
28. If the CBCT imaging after a bleeding episode obscures the radiographic visibility of the tumor such that the ablation probe/tumor relationship is not discernable, the procedure should be terminated.
29. Any presenting condition discovered intra-procedurally that in the opinion of the Investigator would make participating in this study not in the subject's best interest.

Note 1: For Exclusion Criterium 26, the procedure may be attempted again at a later time providing there were no other complications other than an extended navigation time.

Note 2: For Exclusion Criteria 27 and 28, the procedure may be attempted again at a later time, once, in the opinion of the physician, the area of bleeding is fully resolved.

Note 3: For any rescheduled ablations, the ablation should be rescheduled as soon as feasible

but no longer than four weeks after the originally scheduled ablation. Other than INR, other pre-ablation assessments do not need to be repeated.

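### No platelet count is required at the ablation visit or before a rescheduled ablation, so the protocol's own platelet limit cannot be verified when it matters

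*Protocol*

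**What the plan says.** **Eligibility limits.** Exclusion 7 bars a platelet count of 50,000/mm³ or lower and gives no time of measurement. Neighbouring criteria do give one. Exclusion 8 concerns "Subjects with uncorrectable coagulopathy at time of screening", and Exclusion 20 (blood pressure) is tied to Visit 2. Exclusion 10 has an explicit same-day check: "On the day of the procedure, subjects with an INR" above 1.5 may not be treated that day.

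**Scheduled tests.** Table 1, in both the protocol and the SAP, marks the CBC at Visit 1 only. Section 7.1 places Screening within 30 days before Visit 2, accepts standard-of-care laboratory results from that period, and says Screening assessments should not be done on the ablation day. Section 7.2 has the investigator review eligibility again at Visit 2, but its laboratory list is coagulation tests (INR mandatory) and, where applicable, a pregnancy test.

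**Rescheduling.** Section 5.4 Note 2 allows a second attempt after a procedure stopped for bleeding. Note 3 asks that any rescheduled ablation take place promptly, "but no longer than four weeks after the originally scheduled ablation. Other than INR, other pre-ablation assessments do not need to be repeated". Section 6.1 repeats the four-week limit and the waiver for procedures stopped for bleeding. Table 1 note 6 and Section 7.2 instead waive repeats only if ablation follows within two weeks.

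**Systemic therapy.** Exclusion 19 has two limbs: "Subject who received systemic therapy (e.g., chemotherapy, targeted drug therapy, or immunotherapy) within 14 days prior to the planned study ablation procedure", and "those who plan to receive systemic therapy before completing the primary endpoint assessment".

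**The concern.** The platelet limit is one of the protocol's bleeding safeguards, and it is the only numeric laboratory one without a same-day check. INR, PT and APTT do not measure platelets, so the coagulation draw at Visit 2 does not cover it. The investigator must confirm continued eligibility on the day but has no required current result for Exclusion 7.

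The case that matters most is the second attempt. A subject whose first procedure was stopped under Exclusion 27 (bleeding over 50cc, or a Nashville grade 2 or higher intervention) may return with only INR repeated.

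The protocol itself treats bleeding as critical. It stops procedures for it, and "a report of death or severe hemorrhage requiring intervention beyond local therapy" within 30 days of an ablation pauses enrollment. Section 3.0 also reports a death from presumed pulmonary hemorrhage in the sponsor's 10-subject pilot. What is at stake is subject safety; the hypothesis test, sample size and analysis sets are not touched.

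**Working it through.** The plan states no figure of its own on this point. The check sets the requirements side by side and adds up the day windows.

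**1. INR and platelets compared**

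| | INR | Platelets |
|---|---|---|
| Limit | above 1.5 (Exclusion 10) | 50,000/mm³ or lower (Exclusion 7) |
| Timing in the criterion | day of procedure | none |
| Screening | coagulation tests | CBC, up to 30 days before Visit 2 (7.1) |
| Visit 2 pre-procedure | required (7.2) | not listed |
| Rescheduled ablation | repeated | waived (5.4 Note 3, 6.1) |

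**2. Maximum age of the last required platelet count at ablation**

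Age = Screening window + permitted delay.

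- Ablation as scheduled: 30 + 0 = 30 days.
- Rescheduled, with 5.4 Note 3 and 6.1 read literally (four weeks): 30 + 28 = 58 days.
- Rescheduled, if the two-week wording in Table 1 note 6 and 7.2 is taken to cover the CBC: 30 + 14 = 44 days. That wording follows an instruction about ablation-day tests and may not reach the CBC at all.
- Rescheduled, if the 30-day Screening window is re-anchored to the actual ablation date: at most 30 days.
- INR on the same basis: 0 days.

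Under none of these readings is a current count required.

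**3. Could systemic therapy follow the CBC?**

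The first limb of Exclusion 19 and the table in Section 5.5 bar therapy in the 14 days before ablation. With the oldest accepted CBC at day −30, the open interval is 30 − 14 = 16 days, or about 15 if day −14 itself is barred. The second limb may exclude anyone with therapy planned in that interval. It does not reach therapy already given when eligibility is reviewed. Section 2.0 allows standard-of-care Screening tests before consent, so therapy can fall between such a CBC and the eligibility review.

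**4. Scale**

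Section 11.0 classes hemorrhage needing intervention as common, 1% to 10%. For 145 subjects that is 0.01 × 145 = 1.45 to 0.10 × 145 = 14.5 subjects. This covers all such bleeding. The documents do not say what share involves low platelets, or how often a subject would fall to the limit between Screening and ablation, so no event rate follows.

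**The case against.** The strongest reply is that the 58-day figure depends on a doubtful reading. Table 1 and Section 7.1 tie Screening to 30 days before ablation, and the waiver in Note 3 can be taken to mean the Visit 2 pre-procedure tests only. What remains is then a 30-day laboratory window, which is a design choice, and nothing in the documents sets a shorter one. INR has its own reason for a same-day check, because subjects are coming off warfarin. Exclusion 7 may be a Screening threshold only. If it is a continuing criterion, the Visit 2 eligibility review gives the investigator grounds to order a count.

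The therapy route is also narrow, given both limbs of Exclusion 19, the medication update at Visit 2, Exclusion 24 and the required multidisciplinary discussion with a medical oncologist. Other bleeding safeguards exist, and the pilot death is described with prolonged navigation and no mention of platelets.

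Much of this stands. The 58 days is conditional, the therapy route needs a particular sequence, and neither the pilot death nor the 1% to 10% band measures this gap. The gap itself remains: none of these safeguards requires a platelet count, and the 30-day reading still leaves an old value as the only required one. Nor does the warfarin argument explain why a subject returning after a procedure stopped for bleeding needs a new INR and no new platelet count. On the Screening-only reading, the limit gives no assurance on the day bleeding can occur.

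**Conclusion.** The concern holds. No provision in the protocol or SAP requires a platelet count at Visit 2 or before a rescheduled ablation, and 5.4 Note 3 and 6.1 expressly limit required repeats to INR. The last required count can be 30 days old at a scheduled ablation. After a four-week rescheduling it can be up to 58 days old on the literal reading, or at most 30 days if the Screening window governs.

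A subject above the limit at Screening and at or below it on the day could be ablated in full compliance with the plan. How often that would happen cannot be derived from the documents. The conclusion concerns required tests only; sites may well check platelets as routine care. It is a safety improvement that should be made because it is cheap, and it has no bearing on the primary endpoint or its test.

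**What to change.** - Add a platelet count to the Visit 2 pre-procedure laboratory tests in Section 7.2 and in Table 1 of the protocol and SAP. Take it with the coagulation draw and require the result before the procedure starts. Listing it as a Visit 2 test avoids the rule in 7.1 against Screening assessments on the ablation day.
- Name platelets alongside INR as a required repeat in 5.4 Note 3, 6.1, Table 1 note 6 and the matching sentence in 7.2.
- While editing those four places, settle whether two weeks or four weeks applies to the remaining assessments.

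The 50,000/mm³ limit and the 14-day therapy interval stay as they are. The cost is one routine assay per subject (up to 145) and per rescheduled ablation, at a blood draw Visit 2 already requires, plus an occasional postponement and short text edits.

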5.5 Prior and Concomitant Therapy

Subjects may continue with their current medical care throughout the duration of the study, including medications, except as noted in the Exclusion Criteria section of this protocol. All relevant concomitant medications taken within 30 days of Visit 2 and all relevant concomitant medications taken throughout the study, including but not limited to antiplatelet, anticoagulants, chemotherapy, immunotherapies, steroids, anti-inflammatories, NSAIDs, opioids, antibiotics, and medications used to treat adverse events will be recorded on the relevant eCRF page. Components of the anesthesia medication used for the ablation procedure do not need to be recorded on the eCRF page.

In order to avoid confounding the safety and primary effectiveness evaluation, specific treatments/therapies are restricted prior to and after the ablation procedure for given timepoints. The following table summarizes the treatments/therapies restriction timepoints:

Type of Treatment/Therapy	Restriction Prior to Ablation Procedure	Permitted Post Ablation Procedure	Note
Antiplatelet agents (e.g., aspirin, clopidogrel, prasugrel, ticagrelor)	5 days	48-72 hours	Exclusion Criterion #9
Warfarin	3-5 days, or until INR < 1.5	48-72 hours	Exclusion Criterion #10
Anticoagulants (e.g., rivaroxaban, apixaban, dabigatran, edoxaban)		48-72 hours	Exclusion Criterion #11
Lung ablation, surgical resection, radiotherapy, or other treatment procedure	30 days	30 days (or until Primary Endpoint assessed)	Exclusion Criterion #18
Systemic therapy such as chemotherapy, targeted drug therapy (e.g., tyrosine kinase inhibitors), or immunotherapy (e.g., PD-1 antagonists or CTLA inhibitors)	14 days	30 days (or until Primary Endpoint assessed)	Exclusion Criterion #19

After the restriction timepoint, the above-referenced treatments/therapies may be used at the discretion of the PI and treating oncologist, and should be noted in the eCRFs.

5.6 Screen Failures

All subjects signing consent who do not meet all inclusion and exclusion criteria, or who do not have the procedure initiated (i.e., start of navigation to the target tumor(s)), will be recorded as screen failures. The relevant eCRF pages (Demographics, Inclusion/Exclusion Criteria, AEs, Subject Completion/Discontinuation, etc.) will be completed for all screen failure subjects.

Participants who have the navigation initiated but do not receive the microwave ablation will either have the ablation rescheduled, pending cause, or will be considered an intra-operative withdraw/screen fail and will not count toward the 145 subjects enrolled and ablated.

5.7 Removal of Subjects from the Study

In accordance with the current revision of the Declaration of Helsinki and the Code of Federal Regulations, a subject has the right to withdraw from the study at any time for any reason without prejudice to his/her future medical care by the physician or the institution. Should a subject (or subject's legally authorized guardian/representative) decide to withdraw from the study, all efforts will be made to collect any device- or procedure-related AEs or SAEs they may have experienced.

Participation may be terminated prior to completing the study for any of the reasons listed below (reasons that do not fit the categories below will be documented as "other").

Withdrawal of Consent:

If a subject chooses to withdraw early from the study, the eCRF Subject Completion/Discontinuation page should be completed. When a subject's participation is terminated prior to completing the study, the reason for withdrawal is to be documented on the eCRF and in the source documentation.

Investigator Termination:

The Investigator has the right to terminate participation in the study at any time (e.g., for safety or inability to enroll subjects). Should termination of a site be necessary, the Sponsor will provide procedures for termination.

Death:

In the case of subject death, all efforts should be made to get the records documenting the cause of death including postmortem records.

Lost to Follow-Up:

All subjects should be encouraged to return for protocol required clinic visits for evaluation during the study follow-up period. If a subject is unable to return for a clinic visit or unable to be contacted by telephone, attempts to contact the subject should be documented in the source documents. Only after failing to contact the subject at the final follow-up visit, the subject will be considered lost to follow-up and the primary reason for early termination will be completed in the eCRF.

Site Termination or Study Termination:

The Sponsor may terminate a site or the study at any time. When this occurs all subjects at the site will be withdrawn and documented as "early termination." Reasons for site or study termination may include, but are not limited, to the following:

- Administrative concerns (e.g., inadequate subject enrollment, investigator/institution non-compliance, change of business strategy, etc.).
- Safety issues, including those due to non-compliance, which substantially affect the risk-to-benefit ratio of the study subjects at a site or for the study as a whole.
- Regulatory body mandate(s).

6.0 STUDY PROCEDURES

6.1 Procedure Description(s)

Adult subjects with at least one oligometastatic tumor ($\leq 2\text{cm}$) in the lung located in the outer two-thirds and not closer than 1cm to the pleura (including fissures) with colorectal, renal, or sarcoma histology will have transbronchial microwave ablation performed using the MONARCH Platform.

Multidisciplinary Team

With regard to the clinical treatment approach for each patient, this is best assessed and determined by a local (i.e., site) multidisciplinary team (MDT) (aka tumor board) directly caring for the subject. An MDT discussion will be required prior to subject ablation to determine or ensure 1) that all oligometastatic tumors present at Screening are deemed treatable, 2) the manner/timing that all disease sites will be treated, and 3) the appropriateness of subject inclusion in the study. The MDT will include, at a minimum, a medical oncologist, thoracic surgeon or appropriate surgical specialist, and radiation oncologist.

Screening and Planning

A CT scan of the lung is used at Screening to determine tumor details (e.g., size, location, and type, if available). Tumor size must be measured in 3 axes (axial, sagittal, and coronal).

A maximum of two ipsilateral tumors that meet all inclusion and exclusion criteria may be ablated during a single session as part of this protocol. The second tumor may only be ablated if its planned ablation zone does not overlap with the ablation zone of the previously ablated tumor.

If a subject had three oligometastatic tumors that met all inclusion and exclusion criteria, but only two could be treated, per protocol, on the "Ablation Visit", the third, non-target tumor may be ablated at a later study visit. Similarly, if a new, non-target oligometastatic tumor is identified during study follow-up that meets all inclusion and exclusion criteria, it may be ablated. However, only up to three total oligometastatic lung tumors ("target" or "non-target") may be ablated as part of this protocol during the 12-month follow-up period.

If target tumors recur after the original ablation, they may be re-ablated after the Visit 3 assessment for Technique Efficacy has been completed. A re-ablation will not change or extend the follow-up schedule. Additionally, no single tumor should be ablated more than twice during the 12-month follow-up period (i.e., the original ablation procedure and a re-ablation procedure at a separate visit). **Robotic Navigation Portion of Procedure**

Cone beam CT will be used in all cases to confirm the presence of the tumor(s) immediately before initiating the procedure. Navigation to the target tumor(s) will be performed using the MONARCH Platform. The MONARCH Platform is a novel robotic-assisted, software driven, endoscope articulation system which can electromechanically insert, steer, and withdraw a flexible endoscope to patient airways under continuous, real-time, direct, visual control by a physician operator.

Users must follow all instructions for use supplied with the MONARCH Platform, its components, instruments, and accessories, including any instructions for use (IFUs) provided with instruments or accessories. The provided IFU is the primary source for detailed safety information. The MONARCH Platform and its accessories are intended to provide bronchoscopic visualization of and access to patient airways for diagnostic and therapeutic procedures.

Microwave Ablation Portion of Procedure

The ablation will be performed using the NEUWAVE FLEX MC Microwave Ablation System, per the device's User Manual and Instructions for Use (IFU), and the performing physician's clinical judgment.

All ablations will be performed under general anesthesia via a transbronchial approach. Prophylactic antibiotics should be administered pre-ablation per site SOC.

The size of the tumor(s) will be measured and recorded on the day of ablation (Visit 2). Afterwards, the Monarch Platform will be used to navigate the microwave ablation probe to the target tumor and CBCT will be used to confirm probe position/placement.

If the treating physician believes that bleeding during the navigation or ablation requires intervention, or if the bleeding obscures the view of the tumor or ablation zone, the physician is advised to terminate the procedure. The procedure may be attempted again at a later time, once, in the opinion of the physician, the area of bleeding is fully healed. The ablation should be rescheduled within four weeks of the originally scheduled ablation. Other than INR, other pre-ablation assessments do not need to be repeated.

If the target tumor(s) is within approximately 5mm of a major vessel (in the opinion of the treating physician), this tumor should not be ablated, or navigated to, for risk of puncture during the navigation. Additionally, tumors where the anticipated zone of ablation would encompass a significant (in the opinion of the treating physician) emphysematous disease and should also be avoided.

CBCT will be used to guide the microwave ablation probe to the target tumor(s) and ascertain the location of the probe after the robotic bronchoscope has been retracted. CBCT scans will be used at a minimum of three timepoints pre- and post- the ablation process:

- (1) Pre-Navigation: Prior to starting navigation, CBCT will be used to establish baseline imaging, confirm tumor details, and tumor segmentation for navigation (i.e., augmented fluoroscopy).
- (2) Pre-Ablation: Immediately before the ablation, use CBCT to confirm that the probe is in the intended location, and if it is not, reposition the probe.
- (3) Post-Ablation: After completing the ablation, use CBCT to confirm that the ablation margins are adequate.

The smallest and largest length of the entire ablation zone as well as the smallest ablation margin (i.e., distance from the edge of the ablation zone to the edge of the target tumor), must be measured in 3-dimensions and captured in the clinical database.

If a PET scan is taken during the follow-up period, the site must also perform the diagnostic CT as per protocol. PET scans, if obtained, should also be uploaded to the study imaging database with the other required images.

After the ablation procedure, the subject will be observed for up to 23 hours before discharge, except in cases where the Investigator deems it is necessary for the subject to remain hospitalized.

[figure not shown]
For specific details regarding the microwave ablation procedure and workflow between MONARCH and FLEX, please refer to the User Manual.

Tumor Ablation Classification

Ablation classification used for the determination of Technical Success at the time of the final post-procedure scan for a target tumor will be determined using 3-dimensional (3D) assessment (coronal, sagittal, and axial) and defined as:

- A0 = Complete tumor ablation with an ideal minimal margin (i.e., a surrounding minimal margin of at least 5mm).
- A1 = Complete tumor ablation with a minimal margin (i.e., a surrounding minimal margin of less than 5mm but more than 0mm).
- A2 = Incomplete tumor ablation.

While Technical Success will be defined as either an A0 or A1 ablation, the goal is to achieve A0 ablation, and this will be a pre-specified secondary analysis. For all A1 and A2 ablation classifications, the PI will document the reason(s) why a margin of at least 5mm was not attainable on the applicable eCRF.

